**NCT 03265210**

**10/14/2016**

**3c. STATISTICAL ANALYSIS PLAN:** We will examine the distribution and outliers for each variable, and use transformations or bootstrapping if needed. We will test whether baseline demographic and clinical variables are balanced between groups and practices, and adjust in analyses (based on intention to treat principle).

**Aim 3: Reach, Feasibility, Acceptability of Relief and RMH:** We will calculate estimates and 95% CI of the following measures for all subjects and for each sex separately: 1) Reach: Proportions screened, and met study criteria for both conditions. 2) Feasibility: Proportions of patients who initiate Relief and proportion of RMH patients who contact mental health care services; research procedures (timely referrals, assessments) in both conditions; Relief session completion rates and smartphone use. 3) Acceptability to patients: CSQ at baseline, 6, 9, and 12 weeks will be analyzed as in Aim 4. Relief Benchmark tests: >75% session attendance rate, >70% smartphone ratings, and CSQ score  $\geq 3$  (out of 4) will be performed using one-sample z-tests of proportions. We will evaluate clinician and practice staff satisfaction every 6 months.

**Aim 4: Preliminary Effectiveness:** We will use separate linear mixed models for primary and secondary outcomes measured at baseline, 6, 9 and 12 weeks with a subject-specific random intercept and slope and fixed effects for time, treatment, practice, therapist, treatment x time interaction. We will use model building and fitting strategies. In the final model, we will also estimate end of treatment improvements in outcome (from baseline) within each treatment group. As this is an underpowered developmental study, we will control false discovery rate using the Benjamini-Hochberg approach, and not the Family-Wise Error Rate, to adjust for multiple comparisons. Our primary goal will be to estimate effect sizes (or percentage reductions from baseline) with 95% CI and assess clinical significance. Using approaches of Initiative 2.1 (Methods Core), we will conduct exploratory joint analysis of primary and secondary longitudinal outcomes. We will also test between group differences in use of mobile technology measures described in 3b8 above and employing the time series approach of Initiative 2.1 (Methods Core). **Aim 5: Mediation:** For each mediator (MAIA, PANAS, secondary measures) we will use the cross-lagged panel model method to estimate the time-specific and treatment effect on outcomes related to the mediator. In exploratory analysis, we will estimate the indirect effect of longitudinal mediators (Initiative 2.1, Methods Core).

**Exploratory Aim:** We will repeat analyses of Aims 4 and 5 separately for each sex and provide sex-specific estimates of effectiveness and target engagement. We will compare the effect of Relief vs. RMH on quality of life (WHOQL-BREF), on opioid and benzodiazepine use (generalized linear mixed models), and suicidal ideation (MADRS item 10) as in Aim 4. To evaluate cost and potential savings, we will: a) compare the reimbursable and non-billable cost of the interventions, i.e. hours of administrative time, therapists' training, supervision vs. change in use of health care services (assessed by the CSI) by participants in Relief vs. RMH.

**Power:** Consistent with the R34 mechanism, we did not perform power analysis. Instead, we calculated the width of the confidence interval (CI) for estimated effectiveness. We simulated 1000 datasets following a 2-level cluster randomized longitudinal design (N=40 in Relief vs 20 in RMH in 4 practices), a range of intra-class correlations (ICC) and estimated the width of CI for treatment difference (Cohen's d) at week 12 using linear mixed effects regression model. For 80% confidence of the CI, the estimated CI width will be 0.66-0.75. The range of CI width is based on a range of ICCs for level 1 (0.25-0.45) and 2 level (0.05-0.10) clusters. The estimated CI width is consistent with reported CI widths of effectiveness estimates obtained in meta-analyses of RCTs comparing CBT with control conditions in depression.

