- b. Feasibility: Number of patients who initiate Relief or UC/RMH [referral (based on clinical indication) for mental health care] and research procedures (timely referrals, assessments);
- c. Acceptability: Patient's treatment satisfaction at 6, 9, and 12 weeks.

Benchmarks of the study progress: Feasibility: At least 75% of Relief participants will complete Relief. Acceptability: We will obtain treatment satisfaction score at the end of Relief treatment.

- 4. Preliminary Effectiveness: Over the course of 12 weeks, Relief participants, compared to participants in UC/RMH [referral (based on clinical indication) for mental health care], will have greater (effect size) and clinically significant reductions in depression, pain-related disability.
- 5. Preliminary Evidence of Target Engagement/Secondary: The differential effect of Relief vs. UC/RMH in reducing depression and pain-related disability will be independently mediated by reduction of interoceptive focus and positive and negative emotions.

OVERVIEW OF DESIGN

Figure 1.

PROTOCOL

1. Study staff reviews the Electronic Health Records (EHR) on Electronic Privacy Information Center (EPIC) and will identify patients with diagnoses of chronic pain, a DSM 5 diagnoses of depression and anxiety, as well as patients who are on psychotropic and/or pain medications.
2. Study staff will also attend meetings at each of the PCP practices every few months to present/review the study and ask the PCPs to write down the names of any patients they think may be appropriate.
3. Study staff will then contact potential participants via phone. If they meet preliminary eligibility criteria (based on administering the phone screen script) and are interested, they will be invited to come to our offices in White Plains or NYC, or to schedule a video or phone appointment, depending on the circumstances. During the appointment, the consenting process will take place first, and then if the patient consents, the research assistant will conduct the screening assessment (either in person or remotely).
4. RA will then discuss the results of the assessment with [name].
5. If the patient is eligible, the RA will email the data manager with the patient information.
6. The data manager will randomize the patient to either Relief or UC/RMH.
7. The data manager will notify [name] and the supervising therapist (not administering the intervention) about the randomization.

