The research assistant will describe the study, ask potential participants to sign consent, and administer a screening assessment to evaluate eligibility. Once this is confirmed, the research assistant will administer a baseline assessment. At this assessment, the research assistant will explain that follow-up assessments will be administered at 6, 9, and 12 weeks. The research assistant will also explain that the participants will be compensated \$25 for each completed assessment. The research assistant will then facilitate a referral to the data manager, who will identify the participant's group and notify [name], who will notify the appropriate social worker to schedule a meeting.

Inclusion Criteria:

1. 50 years or older
2. PHQ-9 score ≥ 10
3. Chronic pain (most days over the past 3 months)
4. Capacity to consent

Exclusion Criteria:

1. DSM-5 Axis 1 diagnoses other than depression and anxiety disorders (by SCID)
2. Montreal Cognitive Assessment (MoCA) < 24
3. Active suicidal ideation (MADRS item 10 ≥ 4)
4. Severe or life-threatening medical illness

*Note: Patients on psychotropic medications, opioids or benzodiazepines will be included if they do not meet DSM-5 criteria for opioid, anxiolytics or other substance abuse disorders (Human Subjects).

INTERVENTION

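### Change from baseline in treatment satisfaction (CSQ) does not measure acceptability, because the baseline rating precedes treatment assignment and is not in the protocol's schedule

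*SAP*

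**What the plan says.** The two documents give different schedules for satisfaction.

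- **SAP, 3c, Aim 3:** "CSQ at baseline, 6, 9, and 12 weeks will be analyzed as in Aim 4".
- **SAP, 3c, Aim 4:** linear mixed models for outcomes at baseline and the three follow-up visits, with a random intercept and slope and a treatment-by-time interaction. For the final model the SAP adds that "we will also estimate end of treatment improvements in outcome (from baseline) within each treatment group".
- **Protocol, Study Aims, item 3c:** "Acceptability: Patient's treatment satisfaction at 6, 9, and 12 weeks". The benchmark paragraph that follows adds: "We will obtain treatment satisfaction score at the end of Relief treatment". Neither line mentions a baseline rating.
- **Protocol, Research Assessment:** after eligibility is settled, "Once this is confirmed, the research assistant will administer a baseline assessment". Only later in that section comes the step "The research assistant will then facilitate a referral to the data manager, who will identify the participant's group".

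The SAP also sets a Relief benchmark of CSQ at least 3 out of 4. It is tested separately by a one-sample z-test of proportions, and no visit is named for it.

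**The concern.** The Aim 4 model suits symptoms, which exist before treatment and can be expected to change. Satisfaction with a treatment has no value before that treatment is assigned. A CSQ completed at baseline must refer to something else, most plausibly earlier care, and for some patients perhaps nothing. Subtracting it from a week-12 rating of Relief compares ratings of two different things.

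Acceptability is a named aim of this developmental study. If the SAP is followed as written, one of its reported CSQ results will be an improvement in each arm whose size and sign depend on how patients rated something other than the assigned treatment.

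**Working it through.** The plan gives no figure on this point to reproduce. The check has two parts: the order of events, and what the Aim 4 model returns for CSQ.

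**1. Order of events.** Research Assessment runs in the order consent, screening, baseline assessment, referral to the data manager, identification of the group. The numbered steps under Overview of Design agree that assignment follows the eligibility assessment: "The data manager will randomize the patient to either Relief or UC/RMH". No study treatment has been assigned when a baseline CSQ would be completed.

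**2. Within-arm change from baseline.** Assume that mean CSQ in Relief is 3.2 at weeks 6, 9 and 12, and let the baseline mean be B (also assumed). The raw change is 3.2 - B. A straight line through the four visits gives a 12-week change of 1.0286 × (3.2 - B) and a fitted week-12 mean of B + 1.2 × (3.2 - B). Both multipliers are derived in step 3.

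| Assumed B | Raw change | Change, linear time | Fitted week 12, linear time |
|---|---|---|---|
| 2.0 | +1.2 | +1.23 | 3.44 |
| 2.5 | +0.7 | +0.72 | 3.34 |
| 3.0 | +0.2 | +0.21 | 3.24 |
| 3.5 | -0.3 | -0.31 | 3.14 |

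Satisfaction with Relief is the same in every row. The raw-change column is also what a categorical-time model returns, so this problem does not depend on how time is coded.

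**3. Between-arm difference if time is linear.** Assume a true difference of 0 at baseline (expected under randomisation) and D at each follow-up visit.

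- Visits t = 0, 6, 9, 12 have mean 6.75 and deviations -6.75, -0.75, 2.25, 5.25.
- Sum of squares: 45.5625 + 0.5625 + 5.0625 + 27.5625 = 78.75.
- Cross-product with (0, D, D, D): (-0.75 + 2.25 + 5.25) D = 6.75 D.
- Slope: 6.75 D / 78.75 = 0.0857 D per week. Over 12 weeks this is 1.0286 D, or 1.03 D.
- Intercept: 0.75 D - 0.0857 D × 6.75 = 0.17 D, a difference at baseline that does not exist.
- Fitted week 12: 0.1714 D + 1.0286 D = 1.20 D.

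Generalised least squares with several random-intercept and random-slope variances gave the same fitted means as ordinary least squares, so these multipliers do not depend on the variance components.

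**4. Without baseline as an outcome.** A line through D, D, D at weeks 6, 9 and 12 has slope 0 and returns D at week 12. A flat Relief mean of 3.2 is returned as 3.2. Categorical time returns D at each follow-up visit whether or not baseline is in the model.

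**The case against.** A reader might infer that the whole acceptability result is contaminated by satisfaction with earlier care. The documents do not support that.

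- **The randomised contrast survives.** Patients are randomised individually, so baseline ratings are equal between arms in expectation. With categorical time the Relief versus UC/RMH contrast is unbiased. Even with linear time, the interaction over 12 weeks is 1.03 D, close to the truth.
- **Linear time is not stated.** The random slope suggests it, but Aim 4 lists only a fixed effect for time and leaves room for model building. The 1.20 D and 0.17 D come from fitting a line to a step, and any outcome with an early plateau would show the same.
- **The benchmark is separate.** The test of CSQ at least 3 uses a score, not a change. The threshold is the SAP's. The protocol asks only for a score at the end of Relief.
- **A loss of precision is not established.** A reader might expect a baseline rating weakly related to later CSQ to add noise. That holds for a contrast of simple changes from baseline, but the SAP does not commit CSQ to one. Its Power paragraph names the treatment difference at week 12. With categorical time and complete data, baseline adds no variance to that difference.
- **What a baseline CSQ rates is an inference.** Neither document says. The practices' usual care is left in place for UC/RMH, so in that arm the baseline and follow-up ratings may concern much the same service.

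These points limit the concern but do not remove it. Relief cannot be what is rated at baseline. Neither randomisation nor categorical time rescues the within-arm change, and the two schedules still disagree.

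**Conclusion.** The point holds in limited form. The SAP departs from the protocol's satisfaction schedule, and the within-arm CSQ improvement that Aim 4 would produce does not measure acceptability of the assigned treatment. This follows from the sequence of visits alone. Its size is illustrative: with assumed follow-up means of 3.2 and baselines of 2.0 to 3.5, the change runs from +1.2 to -0.3.

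Distortion of fitted levels and of visit-specific arm differences (1.20 D at week 12, 0.17 D at baseline) is conditional on linear time and a constant follow-up difference. The between-arm contrast under categorical time is sound. The benchmark needs only a named visit.

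**What to change.** Reconcile the SAP with the protocol's schedule by replacing the CSQ sentence in Aim 3 with:

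> CSQ at 6, 9 and 12 weeks will be analysed with visit as a categorical factor, reporting arm means and the between-arm difference at each visit. No change from baseline in CSQ is reported. Any baseline CSQ is labelled as satisfaction with prior care and used only descriptively or as a covariate.

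State also that the benchmark of CSQ at least 3 is applied to the end-of-treatment score, which matches the timing in the protocol's benchmark paragraph.

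The change is confined to the CSQ wording in Aim 3 and needs no new data. A baseline CSQ need not be discarded if it is collected. The cost is losing change from baseline as a summary of CSQ.

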[name]	[contact]	[contact]
[name]	[contact]	[contact]

Weill Cornell Medicine Primary Care – Iris Cantor Men’s and Women’s Health Centers

[name]
[name]
[contact]
[contact]

Primary Care Physicians

Name	Email Address	Phone Number
[name]	[contact]	[contact]
[name]	[contact]	[contact]
[name]	[contact]	[contact]
[name]	[contact]	[contact]
[name]		[contact]
[name]	[contact]	[contact]
[name]	[contact]	[contact]

BACKGROUND

Chronic pain and depression frequently co-exist in late and mid-life and contribute to increased disability, high health care costs, psychiatric comorbidity, and suicide. Older and middle-aged depressed-pain patients: a) are mainly treated in primary care practices; and b) are often prescribed medication, which increases the risk for addiction to opioids and benzodiazepines. Despite the need - and desire by the patients and providers - for primary care behavioral interventions, behavioral interventions are scarce in primary care. To address this need, we worked with primary care practices of the Weill Cornell Medical Associates (WCMA), and developed Relief, a 9-session behavioral intervention, designed to be administered by licensed social workers (LCSWs) and/or nurse practitioners (NP) in primary care practices.

Our conceptual model assumes that chronic pain and depression are characterized by an attentional bias assigning greater salience to interoceptive stimuli and to negative emotions along with difficulty shifting attention to goal-oriented/reward-driven state leading to inadequate engagement of the reward network. Accordingly, Relief aims to change the attentional bias of depressed-pain patients favoring interoceptive experiences (discomfort, negative feelings), and increase the salience of newly developed adaptive and rewarding behaviors. Relief also examines patients' expectations of pain treatment (which may be adversely affected by depression), and uses techniques to reduce negative emotions associated with pain treatment, modify unrealistic expectations and enhance the communication between the patient and primary care physician. To facilitate and enhance its delivery, Relief uses easy-to-operate smartphone applications.

[figure not shown]

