In conjunction with psychotherapy sessions, participants will be asked to download, activate, and use a smartphone application designed by *Way to Health*. If participants do not own a smartphone or do not want to use their own phone, we will provide them with a free smartphone to be used for the duration of the study. To maximize the use and benefits of the app, the RA and/or therapist will review its use, prepare written personalized instructions, ask patients for feedback, and repeat the instructions in subsequent sessions as needed.

A smart phone and a Withings watch will be the vehicles for mobile technology interventions.

Augmentation of Relief among participants in the Relief intervention group consists of:

- 1) Daily ratings of mood, interest or pleasure in activities, stress, and pain. A text message sent by Way to Health prompts participants to rate these 4 items on a scale of 1 to 10.
- 2) Daily reminders to pursue preparatory steps and scheduled meaningful, rewarding activities as well as interventions for negative emotions.
- 3) Passive sensing of movement (steps) and sleep daily by the Withings watch. Participants are reminded to review their step count and deep and light sleep duration daily and receive a weekly summary of both on Fridays.
- 4) Participants receive a text message asking them whether they practiced their negative emotions intervention and engaged in their planned rewarding activity and to rate the sense of pleasure (scale 1 to 10) and the sense of satisfaction (scale 1 to 10) they derived.
- 5) At the end of each week, participants receive a text message indicating to them the reward level they achieved. Based on studies of non-depressed older adults by U. Penn investigators, we are using an incentive plan based on behavioral economics.

Participants in the UC/RMH group will also receive a smart phone and Withings watch. They will receive text messages prompting daily ratings of mood, interest or pleasure in activities, stress, and pain

PROCEDURES FOR TREATMENT AFTER STUDY COMPLETION

Participants whose follow up assessments indicate a need for continued mental health services will be provided with mental health referrals. If participants are members of a senior center in the W-MH condition they will automatically receive a referral for mental health services.

DATA MANAGEMENT

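### The Aim 3 benchmark z-tests do not suit their data: attendance and ratings repeat within patient, CSQ has no null proportion, and the protocol's 75% benchmark is a different measure and rule (minor)

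*SAP*

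**What the plan says.** SAP section 3c, Aim 3, sets three benchmarks for the Relief arm: "Relief Benchmark tests: >75% session attendance rate, >70% smartphone ratings, and CSQ score" of 3 or more out of 4. All three "will be performed using one-sample z-tests of proportions". The text gives no unit of analysis, denominator, alpha or sidedness for these tests, and no allowance for repeated records. The same paragraph plans estimates with 95% confidence intervals for the Aim 3 measures, including "Relief session completion rates and smartphone use". The opening of section 3c allows transformation or bootstrapping where needed.

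The protocol describes Relief as "a 9-session behavioral intervention" (Background). Its app collects "Daily ratings of mood, interest or pleasure in activities, stress, and pain" (Way to Health Application). Its benchmarks, under Study Aims, are worded differently from the SAP's. For feasibility: "At least 75% of Relief participants will complete Relief". For acceptability, it says only that a satisfaction score will be obtained when Relief treatment ends, with no threshold. The protocol lists satisfaction at 6, 9 and 12 weeks; the SAP lists CSQ at baseline as well.

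**The concern.** A one-sample z-test of a proportion needs independent yes/no units and a stated null proportion. None of the three benchmarks clearly supplies both.

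- **Attendance and ratings.** A session attendance rate reads most naturally as sessions attended over sessions scheduled, and a rating rate as ratings given over ratings requested. A patient who drops out contributes a run of missed sessions and missed days, so records within a patient are likely to be positively correlated. The binomial standard error ignores this, and the benchmark would be declared met too often.
- **CSQ.** A score of 3 or more defines a responder. It does not say what share of responders to test against.
- **Two 75% benchmarks.** The protocol sets a point threshold on participants who complete treatment, with completion undefined. The SAP sets a significance test on attendance. A reader cannot tell which of them decides feasibility.

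Feasibility and acceptability are stated aims. As the text stands, the unit, the CSQ null and the deciding measure could all be settled after the data are seen.

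**Working it through.** **Inputs from the documents.** Relief arm 40 (SAP, Power: "N=40 in Relief vs 20 in RMH in 4 practices"); 9 sessions per patient (protocol, Background), so 40 × 9 = 360 sessions; nulls 0.75 and 0.70 (SAP, Aim 3).

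**Assumptions.** One-sided 5% test, with two-sided 5% shown for the pass marks. All 40 patients and all 9 sessions are in the denominator. Ratings run for 84 days (12 weeks), with 56 days as an alternative. The within-patient ICC is 0.25-0.45, equal between all records of a patient. That range is the SAP's level-1 ICC in the Power paragraph, given there for the effectiveness simulation and borrowed here. The documents give no ICC for attendance or ratings.

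**The plan's own figures.** No pass mark or power is stated for the benchmarks, so there is none to reproduce. The arm sizes do agree with the Power paragraph: an 80% interval for Cohen's d has width 2 × 1.2816 × √(1/40 + 1/20) = 0.70, inside the stated 0.66-0.75.

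**Pass marks at 75%.** Smallest count x with (x/n − 0.75)/√(0.75 × 0.25/n) above the critical value.

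- Sessions, n = 360, SE = 0.0228: 283 gives z = 1.58 and 284 gives z = 1.70, so one-sided 5% needs 284/360 (78.9%). For two-sided 5%, 286 gives 1.95 and 287 gives 2.07, so 287/360.
- Patients, n = 40: 34 gives 1.46, 35 gives 1.83 and 36 gives 2.19, so 35/40 (87.5%) one-sided or 36/40 two-sided.
- Protocol threshold, applied to the SAP's 40: 0.75 × 40 = 30/40, on completion rather than attendance.

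**Effect of pooling.** Design effect DE = 1 + (m − 1) × ICC for m records per patient. Actual one-sided size ≈ 1 − Φ(1.645/√DE).

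| Records per patient | ICC | DE | Size (formula) | Size (simulated) |
|---|---|---|---|---|
| 9 sessions | 0.05 | 1.40 | 8.2% | 8.1% |
| 9 sessions | 0.25 | 3.00 | 17.1% | 17.2% |
| 9 sessions | 0.45 | 4.60 | 22.2% | 22.9% |
| 84 ratings | 0.05 | 5.15 | 23.4% | 23.8% |
| 84 ratings | 0.25 | 21.75 | 36.2% | 36.9% |
| 84 ratings | 0.45 | 38.35 | 39.5% | 40.3% |

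The simulation is beta-binomial, with 40 patients and 40,000 runs. A repeat with another seed gave 40.6% in the last row, hence the rounded range of 36-41%. With 56 days of ratings and ICC 0.25-0.45, the rate is 33-38%. In the same kind of simulation, a one-sample t-test on the 40 participant proportions had a false-pass rate of 5.6-7.3%.

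**CSQ.** With n = 40 and one-sided 5%, the required number scoring 3 or more depends wholly on the missing null: 26 for a null share of 50%, 30 for 60%, 35 for 75%.

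**The case against.** **The inflation is conditional.** It needs pooled records, a naive standard error and positive within-patient correlation. The ICC range is borrowed, equal correlation between all days is a simplification, and 84 days is assumed. This stands. A reader might infer that the SAP commits itself to an invalid pooled test. It does not say so: each patient could be scored yes/no, and then the inflation disappears. That reading still needs a per-patient cut-off, which the supplied text lacks. SAP section 3b8, cited under Aim 4 for the mobile measures, is not among the supplied documents and may define how ratings are counted.

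**The two documents need not conflict.** A reader might infer that they apply opposing rules to one measure. If true completion were 80%, 30/40 or more would occur in 84% of trials and 35/40 or more in 16%. But the protocol speaks of completing Relief and the SAP of attendance, so that contrast joins two different quantities. A progress target and a later test of something else can coexist. What remains is that neither document says which one decides.

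**The pass marks are not fixed.** The SAP states no alpha. The only confidence level given for Aim 3 is 95%, which would point to the two-sided marks.

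**CSQ timing is not wholly absent.** A reader might infer that no time point exists. The protocol's benchmark text ties the score to the end of Relief treatment, but it does not say which assessment that is.

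**Part of the remedy is already present.** Section 3c plans 95% intervals and allows bootstrapping. It does not say that either is done by participant, and the named benchmark test remains the z-test.

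**Conclusion.** The point holds in limited form, and it is minor.

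- The CSQ benchmark cannot be tested as written. This needs no assumption.
- For attendance and ratings, the literal reading gives false-pass rates of about 17-23% and 36-41% instead of 5%, under the assumptions listed above. Even at an ICC of 0.05 they are about 8% and 23%. Under a participant-level yes/no reading there is no inflation, but there is no cut-off either.
- The protocol's 30/40 and the SAP's 284/360 or 35/40 (two-sided 287/360 or 36/40) are different measures under different rules. They should not be read as a direct contradiction.

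Only the Aim 3 benchmark conclusions are touched. The Aim 4 effectiveness models do not use these tests, and no go/no-go rule in the documents depends on them.

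**What to change.** Amend SAP Aim 3, with matching wording in the protocol:

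1. State alpha and sidedness, and make the participant the unit for both tests and 95% intervals.
2. Attendance and ratings: compute each Relief participant's proportion and compare the mean with 0.75 and 0.70 by one-sample t-test or participant-level bootstrap.
3. CSQ: compare the mean score at the end of Relief treatment with 3 by one-sample t-test, and state which assessment that is.
4. Completion: define it, and report the proportion of participants completing against 75% with an exact 95% interval, as a measure separate from attendance. State which of the two decides the feasibility benchmark.
5. Reconcile whether CSQ is collected at baseline (SAP: yes; protocol: 6, 9 and 12 weeks only).

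This costs wording only and needs no new data. Against pooled records, standard errors rise by √DE: √3.0 to √4.6, or 1.7-2.1 times, for sessions, and √21.75 to √38.35, or 4.7-6.2 times, for 84 days of ratings, at ICC 0.25-0.45. Completion will be imprecise in any case: 30/40 has an exact 95% interval of 59-87%.
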